16.3 Sponsor records

Medtronic will maintain the following records for each site:

- All correspondence which pertains to the investigation
- Signed Investigator Trial Agreements and current curriculum vitae of principal investigator and curriculum vitae of authorized designees where required as well as delegation documentation
- All approved informed consent templates, data review files and Authorization forms and other information provided to the subjects and advertisements, including translations
- Copies of all IRB/MEC approval letters and relevant IRB/MEC correspondence and IRB/MEC voting list/roster/letter of assurance
- Names of the institutions in which the clinical study will be conducted
- Names/contact addresses of monitors
- Statistical analyses and underlying supporting data
- Final report of the clinical study
- The Clinical Investigation Plan
- Study training records for site personnel and Medtronic personnel involved in the study
- Insurance certificates
- Any other records that local regulatory agencies require to be maintained.

16.4 Sponsor reports

Medtronic shall prepare and submit the following complete, accurate, and timely reports listed in the tables below (by geography). In addition to the reports listed below, Medtronic shall, upon request of reviewing IRB/EC, regulatory agency or FDA, provide accurate, complete and current information about any aspect of the investigation. Medtronic reporting requirements for safety data are listed in Table 7 of the Adverse Event section.

Participating sites will have access to their own study data for ad hoc reporting.

Table 11: Sponsor Reports

Report	Submit to	Description
Progress Report	
 Regulatory Authority 	Progress reports will be submitted to regulatory authority as required, and to physicians & Ethics Boards as requested.
Withdrawal of Ethics Board approval	
 Participating Sites Regulatory Authority 	Notification within five working days after the sponsor first learns of the withdrawal of approval. To be reported to Regulatory Authorities as required.
Final report	
 Investigators, IRB/MEC 	A final report will be submitted to the investigators and IRBs/MECs within three months after completion or termination of this study.
Study deviation	
 Investigators 	Site specific study deviations will be submitted to investigators periodically.

Medtronic records and reports will be maintained in a password-protected document management system, and paper documents (where applicable) will be stored in stored in secured file cabinets at Medtronic during the course of this study. After closure of the study Medtronic will archive records and reports indefinitely.

Appendix A: Draft data collection elements (Case Report Forms)

Draft Case Report Forms for the Reveal LINQ Registry will be provided under separate cover upon request. Final CRFs will be provided to sites via the electronic data management system after the site has fulfilled all requirements for database access.

Appendix B: Publication plan

Publications from the Reveal LINQ Registry study will be handled according to Cardiac Rhythm Heart Failure Standard Operating Procedures and as indicated in the Clinical Trial Agreement.

Publication Committee

The Reveal LINQ Registry study team has formed an Oversight Committee. This committee will manage study publications with the goal of publishing findings from the data. The Oversight Committee Charter is available under separate cover.

Membership in the Publication Committee does not guarantee authorship. The committee will meet at regular intervals, as needed.

Management of Primary, Secondary and Ancillary Publications

The Oversight Committee, with Medtronic representatives will serve as the Publication Committee. The Publication Committee reviews, prioritizes, and manages all publications including primary, secondary and ancillary publications. Primary and secondary publications are those that address analyses of any or all primary objectives or ancillary objectives, respectively, as specified in the Clinical Investigation Plan.

An ancillary publication is any publication that does not address the study objectives identified in the Clinical Investigation Plan. They include publications proposed and developed by other Medtronic departments or entities, clinicians participating in this clinical study, and clinicians not participating in this clinical study. The committee will work with Medtronic to ensure that requests do not present conflicts with other proposals, are not duplicative, and to determine which ancillary publication proposals, if any, will be supported.

The committee may decide that no publications, including abstracts, will be published prior to the end of the study or with individual site data. Requests for publications on study objectives utilizing subset data (e.g., regional) will be evaluated for scientific validity and the ability of Medtronic to provide resources.

Criteria for Determining Authorship

Publications will adhere to authorship criteria defined by the International Committee of Medical Journal Editors (ICMJE, Uniform requirements for manuscripts submitted to biomedical journals, www.icmje.org) in addition to Medtronic authorship criteria. Individual authorship criteria defined by the target journal or conference will be followed when it differs from ICMJE criteria.

Decisions regarding authorship and contributor-ship will be made by the committee. The selected authors will be responsible for drafting the publication. All selected authors must fulfill the authorship conditions stated above to be listed as authors, and all contributors who fulfill the conditions must be listed as authors.

All investigators not listed as co-authors will be acknowledged as the “Medtronic Reveal LINQ Registry Clinical Study Investigators” and will be individually listed according to the guidelines of the applicable scientific journal when possible and affiliation. Any other contributors will be acknowledged by name with their specific contribution indicated.

Transparency

Transparency of study results will be maintained by the following means:

- a final report, describing the results of all objectives and analysis, will be distributed to all investigators, MECs and Competent Authorities of participating countries when required by local law
- registering and posting the study results on ClinicalTrials.gov based on the posting rules stipulated as well as local regulatory databases where required by local law
- disclosing conflicts of interest of the co-authors of publications according to the policies set forth by the corresponding journals and conferences
- making an individual sites study data accessible to the corresponding investigator after the completion of the study, if requested

Appendix C: Informed consent templates and Data Review Files

Geography-specific PIC and DRF templates will be provided under separate cover.

Appendix D: Participating Investigators and Institutions

A complete list of participating investigators and institutions where the study activities will be conducted will be provided under a separate cover.

Appendix E: Ethics Committee List

A complete list of participating Ethics Committees and their Chairperson(s) will be distributed under a separate cover when available.

Appendix F: Additional information for Japanese centers

Other required information for Japanese centers, such as detailed contact information of Medtronic Japan, names of monitors, detailed CRF instruction, etc. not outlined in the Clinical Investigational Plan will be provided under a separate cover.

Appendix G: Committees

The Reveal LINQ Registry study will utilize an Oversight Committee to manage study publications. Committee membership rosters will be maintained at Medtronic and will be made available upon request.

A Data Monitoring Committee (DMC) is not needed for this study. The study is considered non-significant risk for study participants, thus the need for additional safety oversight beyond Medtronic's already rigorous safety monitoring processes is not required.

Appendix H: Labeling

Labeling and package for all products used in this study will follow the local regulatory requirements.

Labeling and reference/technical manuals for the Reveal LINQ will be provided under separate cover. Labeling for all other market approved system components can be found with each package insert.

Appendix I: Definitions

Abnormal Battery Depletion: Any battery depletion rate which is faster than expected given an implanted devices programmed settings or usage conditions.

Atrial Fibrillation: Atrial Fibrillation is a supraventricular tachyarrhythmia characterized by uncoordinated atrial activity with consequent deterioration of atrial mechanical function. On the electrocardiogram (ECG), atrial fibrillation is characterized by the replacement of consistent P waves with rapid oscillations or fibrillation waves that vary in amplitude, shape and timing, associated with an irregular, frequently rapid ventricular response when atrioventricular conduction is intact.

Atrial Flutter: Atrial Flutter is characterized by a sawtooth pattern of regular atrial activation called flutter waves on the ECG, particularly visible in leads II, III, aVF and v1

Bleeding Event- An episode of internal or external bleeding classified into the following categories:

Life-threatening/disabling – fatal bleeding (BARC type 5) or bleeding in a critical organ, such as intracranial, intraspinal, intraocular, or pericardial necessitating pericardiocentesis, or intramuscular with compartment syndrome (BARC type 3b and 3c) or bleeding causing hypovolemic shock or severe hypotension requiring vasopressors or surgery (BARC type 3b) or overt source of bleeding with drop in hemoglobin of > 5g/dL or whole blood or packed red blood cells (RBCs) transfusion >4 units (BARC type 3b)

Major bleeding (BARC type 3a) – overt bleeding either associated with a drop in the hemoglobin level of at least 3.0 g/dL or requiring transfusion of 2 or 3 units of whole blood/RBC, or causing hospitalization or permanent injury, or requiring surgery AND does not meet the criteria of life-threatening or disabling bleeding

Minor bleeding (BARC type 2 or 3a depending on severity) – any bleeding worth of clinical mention (e.g. access site hematoma) that does not qualify as life-threatening, disabling, or major

Cardiac Arrest: cardiac arrest is the sudden cessation of cardiac activity so that the victim becomes unresponsive, with no normal breathing and no signs of circulation. If corrective measures are not taken rapidly, this condition progresses to sudden death. Cardiac arrest should be used to signify an event as described above that is reversed, usually by CPR, and/or defibrillation or cardioversion, or cardiac pacing. Sudden cardiac death should not be used to describe events that are not fatal.

Cardiovascular Mortality: Any of the following criteria:

- Death due to proximate cardiac cause (e.g. myocardial infarction, cardiac tamponade, worsening heart failure)
- Death caused by non-coronary vascular conditions such as neurological events, pulmonary embolism, ruptured aortic aneurysm, dissecting aneurysm, or other vascular disease
- All procedure-related deaths, including those related to a complication of the procedure or treatment for a complication of the procedure
- All valve related deaths including structural or nonstructural valve dysfunction or

- other valve related adverse events
- Sudden or unwitnessed death
- Death of unknown cause

Non-Cardiovascular Mortality: Any death in which the primary cause of death is clearly related to another condition (e.g. trauma, cancer, suicide)

Clinical Performance (ISO14155-2011): Behavior of a medical device or response of the patient(s) to the medical device in relation to its intended use, when correctly applied to appropriate patient(s).

Data Query: A standard form used to request clarification of Registry collected data

Death:

- Sudden cardiac: Witnessed instantaneous in a previously stable subject. This may occur with or without preceding signs or symptoms, or may occur immediately following sudden dyspnea, lightheadedness, or palpitations.

Unwitnessed. Subject found dead who at time of last witnessed contact was in usual state of health without medical complaints or obvious difficulty. This applies to subjects dying during sleep. Note: Whereas most sudden deaths seem to result from cardiac arrhythmias, sudden death may also result from non-cardiac processes (e.g., acute pulmonary embolus, rupture of abdominal aortic aneurysm). In most cases, documentation of the actual cause of death is missing.

- Non-sudden cardiac. Includes deaths of subjects in acute pulmonary edema; with severe, progressive HF; cardiogenic shock; or after recent cardiac surgical procedure.
- Non-cardiac. Vascular death (thromboembolic event, acute hemorrhage, CVA, dissecting aneurysm), or non-cardiovascular death (e.g., trauma, renal failure, cancer, sepsis, suicide).
- Unknown. No information available regarding death event.

Deviation: instance(s) of failure to follow, intentionally or unintentionally, the requirements of the clinical plan (Protocol and associated Addendum (if applicable)).

Device Data: stored data from a medical device saved to a media (e.g. USB, floppy disk) which is transferable to a data management system or data directly transferred to a data management system via a direct upload or transmission e.g. pacemaker, ICD, neurostimulator, etc.

Echocardiography (Echo): Diagnostic method which uses sound waves to record imaging of the heart and the heart's movement. Transthoracic Echo is done through the chest wall while transesophageal echo is done through the esophagus

Electrical Data: Data that describes the electrical characteristics of some medical devices including, but not limited to: impedance, threshold, and sensing amplitude measurements e.g. implanted cardiac rhythm devices

Failure to Sense/Undersensing (cardiac): Intermittent or complete loss of sensing or failure to detect the intended intrinsic cardiac signals (atrial or ventricular) during non-refractory periods at programmed sensitivity settings.

Heart Failure: Heart failure is defined as physician documentation or report of any of the following clinical symptoms of heart failure described as unusual dyspnea on light exertion, recurrent dyspnea occurring in the supine position, fluid retention; or the description of rales, jugular venous distension, pulmonary edema on physical exam, or pulmonary edema on chest x-ray. A low ejection fraction alone, without clinical evidence of heart failure does not qualify as heart failure.

Hospitalization: An overnight hospital admission, where admission date and discharge date are different

Implanted: When surgical incisions are closed (implant pocket closed).

Insertable/Implantable Loop Recorder (ILR) / Insertable Cardiac Monitor: A programmable device which continuously monitors a patient's ECG and other physiological parameters and used to aid in the diagnosis of a suspected cardiac arrhythmia

Lost to Follow-Up: A subject who will no longer be followed in the Registry due to unwillingness or inability to return to the clinic for follow-up or a subject who cannot be located for subsequent follow-up

Oversensing (cardiac): Misinterpretation of cardiac or non-cardiac events as cardiac depolarization, (e.g. T-waves, skeletal muscle potentials, lead noise, and extra cardiac electromagnetic interference (EMI)).

Procedure-Related Event: An adverse event that occurs that is directly related to the implantation or modification of the Reveal LINQ system.

Programmer Upload: The electronic transfer of device data from a device programmer to the data management system.

Remote Data Transmission: secure transmission of stored medical device data to clinics, physicians, and/or Medtronic, i.e. Medtronic's CareLink Network

Stroke: Loss of neurological function caused by an ischemic or hemorrhagic event with residual symptoms lasting at least 24 hours after onset or leading to death

Syncope: Sudden loss of consciousness with loss of postural tone, not related to anesthesia, with spontaneous recovery as reported by patient or observer. Patients may experience syncope when supine

Transient Ischemic Attack: A focal neurological deficit (usually corresponding to the territory of a single cerebral vessel) that resolves spontaneously with any evidence of residual deficit at 24 hours.

Undersensing: Intermittent or complete loss of sensing or failure to detect the intended intrinsic cardiac signals (atrial or ventricular) during non-refractory periods at programmed sensitivity settings, see also Failure to Sense.

Ventricular Tachycardia: Ventricular Tachycardia is a cardiac arrhythmia of 3 or more consecutive complexes in duration emanating from the ventricles at a rate of >100 bpm (cycle length: <600 ms).

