9.1 Adverse Event Assessment

9.1.1 Adverse Events

AE definitions are provided in Table 5. AEs that are potentially system related or procedure related as well as stroke, TIA, bleeding events, and ablation-related events will be collected and reported to Medtronic during the study, starting from the time the subject completes consent. Reporting of these events to Medtronic will occur on the AE eCRF.

Each AE must be recorded on a separate AE eCRF and include a description of the event, the diagnosis, the date of event onset, the date the site became aware of the event, the relatedness and seriousness of the event, diagnostic tests and procedures performed, actions taken as a result of the event, and the outcome of the event. Documented pre-existing conditions are not considered AEs unless the nature or severity of the condition has worsened. Additionally, detected arrhythmias (including AF) for which no intervention is made are not reportable as AEs. In all geographies, Unavoidable AEs, listed in Table 5 need not to be reported if resolved within the timeframe specified.

For AEs that require immediate reporting (see Table 7), initial reporting may be done by phone, or on the CRF completing as much information as possible. The AE CRF must be completed as soon as possible.

In case the investigator requires information from the sponsor in an emergency situation, the investigator can contact the study sponsor (Table 1).

An assessment for Device Related, Procedure-Related Events as well as stroke, TIA, bleeding events, and ablation-related events will be conducted at each subject follow-up. Submit any

additional supporting evidence which could assist in the assessment and review of reported events e.g. device transmissions and/or device uploads.

9.1.2 *Device Deficiencies*

Device deficiency information will be collected throughout the study and reported to Medtronic. Device deficiencies that did not lead to an Adverse Event should be reported as a device deficiency only.

9.1.3 *Processing Updates and Resolution*

For any changes in status of a previously reported AE (i.e. change in actions taken, change in outcome, change in relatedness), an update to the original AE must be completed. All reported AEs must be followed until the AE has been resolved, is unresolved with no further actions planned, the subject exits the study or until study closure, whichever occurs first.

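### The bleeding severity classes leave exactly 4 transfused units unassigned, so such a bleed with no other upper-class criterion is graded minor, below a 2-unit bleed

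*Protocol*

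**What the plan says.** Protocol section 9.1.1 makes bleeding reportable in its own right: "AEs that are potentially system related or procedure related as well as stroke, TIA, bleeding events, and ablation-related events will be collected". Section 9.2 sends the reader to Appendix I for event definitions, and sections 9.2 and 9.3 say that adverse events are classified by the definitions given. The Appendix I wording is therefore the operative rule.

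Appendix I defines three bleeding classes:

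- **Life-threatening/disabling.** Several alternative criteria. The two numerical ones are "overt source of bleeding with drop in hemoglobin of > 5g/dL" and, for transfusion, "packed red blood cells (RBCs) transfusion >4 units (BARC type 3b". The others cover fatal bleeding, bleeding into a critical organ, and shock or severe hypotension.
- **Major.** Again several alternatives. The hemoglobin criterion is a fall of 3.0 g/dL or more. The transfusion criterion reads "requiring transfusion of 2 or 3 units of whole blood/RBC". The remaining routes are a hospital stay brought on by the bleed, lasting injury, and the need for an operation. An event that already belongs in the higher class is excluded.
- **Minor.** A residual class: bleeding worth clinical mention "that does not qualify as life-threatening, disabling, or major".

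Appendix I also defines hospitalization: "An overnight hospital admission, where admission date and discharge date are different".

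SAP section 6.10 plans to summarize adverse events by relatedness, seriousness and primary diagnosis. Its visible text does not mention bleeding class.

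**The concern.** A severity scale should not give a lower grade for more of the same severity marker. Here the transfusion criterion stops at 3 units in one class and resumes above 4 in the next, and nothing in either document assigns the value between. Because minor is defined by exclusion, the gap does not leave the event ungraded. It drops the event to the lowest class.

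The hemoglobin criteria in the same definition meet without a gap, which suggests that the transfusion gap is a drafting slip and not a deliberate choice. What is at stake is the grade of individual bleeding events, and the consistency of any listing or publication that sorts bleeds by these classes.

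**Working it through.** There is no plan figure to reproduce. The check is to write the three definitions as one decision rule and apply it to each value.

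**Inputs** (all from Appendix I). U = whole units transfused; H = hemoglobin fall in g/dL.

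- Life-threatening if H > 5, or U > 4, or another listed life-threatening criterion is met.
- Major if not life-threatening, and H ≥ 3.0, or U is 2 or 3, or the bleed caused hospitalization or permanent injury, or required surgery.
- Minor if neither.

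**Transfusion alone** (H below 3.0, no other criterion met):

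| Units | Class |
|---|---|
| 0 | Minor |
| 1 | Minor |
| 2 | Major |
| 3 | Major |
| 4 | Minor |
| 5 or more | Life-threatening |

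At U = 4, the test U > 4 fails and the test U = 2 or 3 fails, so the residual rule applies. The grade drops one class from 3 to 4 units and rises two classes from 4 to 5.

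**Hemoglobin alone** (no transfusion, no other criterion met):

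| Fall in g/dL | Class |
|---|---|
| Below 3.0 | Minor |
| 3.0 to 5 | Major |
| Above 5 | Life-threatening |

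Every value has one class and the order is never reversed.

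**Exactly 4 units combined with other criteria:**

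| Added feature | Class |
|---|---|
| H from 0 to 2.9, nothing else | Minor |
| H from 3.0 to 5 | Major |
| H above 5 | Life-threatening |
| Hospitalization, with H below 3.0 | Major |

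Permanent injury or surgery likewise gives at least major, because the criteria are alternatives. The misgrading is thus confined to the first row of the last table.

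**The case against.** The strongest reply is that the gap has little to act on.

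- **Other routes catch most cases.** The criteria are joined by *or*, so a 4-unit bleed will often be graded major or higher through the hemoglobin fall or an overnight admission. A reader might infer that every 4-unit bleed becomes minor. The text does not support that, and the condition that no other criterion is met is essential. The routes do not close the gap, however. For example, the major class asks that the bleed cause hospitalization and, unlike the serious adverse event definition in Table 5, does not mention prolonging an existing one.
- **No planned output is shown to depend on the class.** A reader might infer that reported counts of major and life-threatening bleeding will be too low. No visible text plans such counts. SAP section 6.10 does not use the class, and Table 6 of the protocol contains no bleeding scale. Its sponsor label for life-threatening events is not tied to the Appendix I classes. Seriousness is judged separately, and a 4-unit bleed is still reported whatever its grade. The ancillary analyses are redacted, so a use there can be neither shown nor excluded.
- **The primary objectives are untouched.** It is tempting to link bleeding grade to medication changes after detection of atrial fibrillation. Primary Objective #1 counts diagnoses and the treatments linked to them, and bleeding grade does not enter it. Primary Objective #2 concerns infection.
- **The BARC labels prove nothing further.** Type 3a appears against both major and minor, in the latter case depending on severity. The classes are defined by their criteria, and a cross-reference between two scales need not be one-to-one. The double label does not settle where 4 units belongs, but it is not shown to be an error.
- **One character matters.** If the strict inequality was meant to be ≥, the gap disappears. The sign ≥ is used elsewhere in the protocol (section 12.2), and correcting the sign would itself be a repair of the kind asked for.

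These points bear on priority. None of them assigns exactly 4 units to an upper class.

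**Conclusion.** The definition is wrong as written at one value. A bleed with exactly 4 units transfused and no other major or life-threatening criterion is graded minor, one class below a 2- or 3-unit bleed and two below a 5-unit bleed.

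This rests on a literal reading of Appendix I and on whole-unit transfusions. The number of affected events cannot be computed, because the documents give no bleeding or transfusion frequencies; it is likely to be small. On the visible text the consequence stops at the grading of individual bleeds and any report that uses it. No bias in a primary result or in a planned safety table is shown.

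**What to change.** Reconcile the two transfusion cut-offs in Appendix I so that every unit count falls in exactly one class and severity does not fall as units rise. Either boundary could be moved to close the gap. Which class takes 4 units is for the sponsor to decide, since the documents give no basis for choosing.

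Then check any bleeding events already classified for which 4 units is recorded, and apply the corrected rule to them. This is possible only if units are captured. The adverse event form contents listed in section 9.1.1 do not name transfusion units, and the case report forms are supplied separately (Appendix A), so the sponsor should confirm this first.

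The cost is a one-line correction to a definition and a short review of the bleeding events held. No sample size, endpoint or analysis in the visible SAP changes.
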